4.2.2. Cemiplimab and Plerixafor-Related Adverse Events

4.2.2.1 Cemiplimab Related Adverse Events

Blocking PD-1 may permit the emergence of auto-reactive T cells and resultant clinical autoimmunity. Rash/pruritus, diarrhea/colitis, pneumonitis, hepatitis, and hypothyroidism were drug-related, presumptive autoimmune events noted in previous anti-PD-1 studies.

For the purposes of this study, a cemiplimab-related AE is defined as an AE of unknown etiology, associated with drug exposure and is consistent with its known toxicity profile. Efforts should be made to rule out neoplastic, infectious, metabolic, toxin or other etiologic causes. Serological, immunological, and histological (biopsy) data should be used to support the diagnosis of an immune-mediated toxicity. Suspected AEs must be documented on an AE or SAE CRF. Identification and treatment of cemiplimab-related AEs can be found in the NCCN's guidelines for the management of immunotherapy-related toxicities. Additional guidance can be found in the cemiplimab Investigator's Brochures (IB).

Subjects who experience a grade 3 or higher related AE should be discussed with the Protocol Chair immediately.

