6.2. Relationship

The relationship of an AE to the administration of the study drug is to be assessed by the investigator according to the following definitions:

- No (unrelated, not related, no relation): The time course between the administration of study drug and the occurrence or worsening of the adverse event rules out a causal relationship and another cause (concomitant drugs, therapies, complications, etc.) is suspected.
- Yes (related): The time course between the administration of study drug and the occurrence or worsening of the adverse event is consistent with a causal relationship and no other cause (concomitant drugs, therapies, complications, etc.) can be identified.

The following factors should also be considered:

- The temporal sequence from study drug administration - The event should occur after the study drug is given. The length of time from study drug exposure to event should be evaluated in the clinical context of the event.
- Underlying, concomitant, intercurrent diseases - Each report should be evaluated in the context of the natural history and course of the disease being treated and any other disease the subject may have.
- Concomitant medication - The other medications the subject is taking or the treatment the subject receives should be examined to determine whether any of them might be recognized to cause the event in question.
- Known response pattern for this class of study drug - Clinical and/or preclinical data may indicate whether a particular response is likely to be a class effect.

- Exposure to physical and/or mental stresses - The exposure to stress might induce adverse changes in the recipient and provide a logical and better explanation for the event.
- The pharmacology and pharmacokinetics of the study drug - The known pharmacologic properties (absorption, distribution, metabolism, and excretion) of the study drug should be considered.

Assessment of Grade:

The investigator will make an assessment of grade for each AE and SAE reported during the study, which will be recorded in the CRF. The assessment will be based on the National Cancer Institute's CTCAE (Version 5.0) and graded as shown below:

- Grade 1: Mild; asymptomatic or mild symptoms; clinical or diagnostic observations only; intervention not indicated
- Grade 2: Moderate; minimal, local or noninvasive intervention indicated; limiting age-appropriate instrumental activities of daily living

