6.3. Expectedness

Unexpected AE: An AE, which varies in nature, intensity or frequency from information on the investigational drug/agent provided in the product IB, package insert or safety reports. Any AE that is not included in the IB, package insert, safety reports or informed consent is considered “unexpected”. An expected AE with a fatal outcome should be considered unexpected unless the IB specifically states that the AE might be associated with a fatal outcome.

Expected (known) AE: An AE, which has been reported in the IB, package insert or safety reports. An AE is considered “expected”, only if it is included in the IB document as a risk.

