6.4. Handling of Expedited Safety Reports

In accordance with local regulations, Sanofi will notify investigators of all SAEs that are unexpected (i.e., not previously described in the IB), and related to plerixafor and cemiplimab. An event meeting these criteria is termed a Suspected, Unexpected Serious Adverse Reaction (SUSAR). Investigator notification of these events will be in the form of a SUSAR Report that is to be e-mailed to the investigators and the study coordinators. Upon receiving such notices, the investigator must review and retain the notice with the IB and where required by local regulations, the investigator will submit the SUSAR to the appropriate IRB. The investigator and IRB will

determine if the informed consent requires revision. The investigator should also comply with the IRB procedures for reporting any other safety information.

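### Sections 4.2.2.1 and 6.2 define relatedness to cemiplimab differently, so an event new in nature can be related under one and not cemiplimab-related under the other

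*Combined protocol and SAP*

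**What the plan says.** Section 4.2.2.1 opens its definition with "For the purposes of this study, a cemiplimab-related AE is defined as". The definition itself is that "a cemiplimab-related AE is defined as an AE of unknown etiology, associated with drug exposure and is consistent with its known toxicity profile", which sets three joint conditions: unknown etiology, association with exposure, and agreement with the drug's known toxicity profile. The scope is the study as a whole, not only the management of immune-mediated events.

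Section 6.2 gives the investigator a yes/no causality rule. An event is related when its time course "is consistent with a causal relationship and no other cause (concomitant drugs, therapies, complications, etc.) can be identified". The known response pattern of the drug class appears afterwards, in a list of further factors to consider: "Clinical and/or preclinical data may indicate whether a particular response is likely to be a class effect".

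Section 6.3 deals with expectedness. It covers "An AE, which varies in nature, intensity or frequency from information on the investigational drug/agent", and it also treats an expected event with a fatal outcome as unexpected unless the investigator's brochure (IB) says that the event may be fatal.

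Section 6.4 combines the two ideas. A SUSAR is drawn from "SAEs that are unexpected (i.e., not previously described in the IB), and related to plerixafor and cemiplimab".

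**The concern.** Agreement with the known profile is a test of whether an event is expected. Section 4.2.2.1 uses it as a test of whether the event is caused by the drug. The trial adds CXCR4 blockade to PD-1 blockade, and a secondary objective is to characterize the toxicity of the combination, so events outside the single-agent profile are of particular interest.

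Attribution is used in several places:

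- SUSAR classification under 6.4.
- The secondary safety endpoints in 10.2 that count drug-related toxicities, including those of grade 3 or above.
- Reporting of SAEs after the follow-up periods, which 6.5.1 limits to events considered related.
- Possibly the run-in and 33% rules. Section 4.7 defines unacceptable toxicity through 4.10.2, and most of the specific toxicity criteria there apply to drug-related or treatment-related events.

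The SAE form in Appendix D asks about relatedness to each drug separately, so an investigator filling in the cemiplimab box has two rules that can give different answers.

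**Working it through.** **Comparing the definitions.** Take a serious event that is new in nature, has a compatible time course and has no other identifiable cause.

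| Section | Test | Result |
|---|---|---|
| 6.2 | Time course fits, no other cause | Related |
| 4.2.2.1 | Unknown etiology, exposure, and fits known profile | Not cemiplimab-related (third condition fails) |
| 6.3 | Differs in nature from the IB | Unexpected |
| 6.4 | Serious, related and unexpected | SUSAR if 6.2 governs; not a cemiplimab SUSAR if 4.2.2.1 governs |

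Now take an event within the known profile but more severe or more frequent than described, or unexpectedly fatal. It can meet all three conditions of 4.2.2.1 and still be unexpected under 6.3. A cemiplimab SUSAR therefore remains possible for such events, and the conflict is strict only for events new in nature.

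**Checking the stopping rule.** Section 12.2 stops enrollment at 2 events in 6 patients, 3 in 7–9, 4 in 10–12, and so on to 13 in 37–39. The boundary is b(6) = 2 and b(k) = integer part of (k + 2)/3 for k from 7 to 39. Let q(k, x) be the probability of x events after k patients without having stopped, and p the risk per patient. Then

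q(k, x) = q(k−1, x)(1 − p) + q(k−1, x−1)p,

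and from k = 6 onward the mass at x ≥ b(k) is removed and added to the halt probability.

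Reproducing the plan's table, which rests on 5000 simulations:

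| True risk | Printed halt % | Exact halt % |
|---|---|---|
| 0.10 | 12.4 | 13.0 |
| 0.20 | 45.8 | 44.4 |
| 0.33 | 85 | 86.2 |
| 0.40 | 96.3 | 96.3 |

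The exact values agree with the printed ones to within 2 points.

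**Illustration of undercounting.** If a share f of qualifying events is not counted, the rule acts on p(1 − f). The documents give no f, so every value below is an assumption.

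| True p | f | p(1 − f) | Exact halt % |
|---|---|---|---|
| 0.20 | 0 | 0.20 | 44.4 |
| 0.20 | 5% | 0.19 | 40.7 |
| 0.20 | 25% | 0.15 | 27.1 |
| 0.20 | 50% | 0.10 | 13.0 |
| 0.40 | 0 | 0.40 | 96.3 |
| 0.40 | 10% | 0.36 | 91.7 |
| 0.40 | 25% | 0.30 | 78.7 |
| 0.40 | 50% | 0.20 | 44.4 |

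The 0.40 rows are the more telling, because that risk lies above the 33% limit the rule is meant to guard. In the run-in, a single uncounted event turns 2 of 6 (halt) into 1 of 6 (continue).

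**The case against.** The strongest reply is that 6.2 is the operative rule. Section 4.2.2.1 sits under supportive-care guidance, and the surrounding text is about ruling out other causes and diagnosing immune-mediated toxicity. Section 6.2 says that the investigator is to assess relationship by its definitions, and Section 11 sends readers to Section 6 for AE guidelines. This makes 6.2 the more natural choice, but no sentence gives it precedence, and 4.2.2.1 claims study-wide scope.

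Three further points stand and limit the reach.

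- **Stopping rule.** A reader might infer that a new toxicity of the combination cannot count toward the run-in or 33% rules. The documents do not support that. Section 4.10.2 speaks of drug-related or treatment-related events, not cemiplimab-related ones. Such an event may be attributed to plerixafor, or to study drug generally under 6.2. The plerixafor section, 4.2.2.2, is blacked out, so its wording cannot be held against the plan. Section 4.10.2 also lets any AE qualify if the investigator judges that it poses substantial clinical risk, with no relatedness test.
- **Reporting delay.** A reader might infer that expedited reporting is delayed. Section 6.5.1 requires all SAEs to go to the Protocol Chair and the supplying company within 24 hours, up to 100 days after the last dose or new antineoplastic treatment, whatever their attribution. (Study calendar note 22 mentions only related SAEs at the 100-day contact, but 6.5.1 and 4.12.1 cover all.) All AEs are captured, related or not.
- **SUSARs.** A reader might infer that a cemiplimab SUSAR is all but impossible. Section 6.3 shows otherwise for differences in intensity or frequency and for unexpectedly fatal events.

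**Conclusion.** The two definitions conflict and must be reconciled. Taken literally, 4.2.2.1 denies attribution to cemiplimab for an event new in nature that 6.2 would call related, and with it a cemiplimab SUSAR classification. The consequences fall on that classification, on the drug-related toxicity endpoints, on SAEs after the follow-up periods, and possibly on the related-event criteria of 4.10.2.

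The effect on the halt probability cannot be sized from the documents. The calculated drops assume both a share of uncounted events and that each of those events misses every other route: attribution to plerixafor, attribution to study drug, and investigator judgment. They show direction and sensitivity, not an expected loss. The sample size, type I error and power of the two-stage design are unaffected.

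**What to change.** Delete from 4.2.2.1 the clause that makes agreement with the known toxicity profile a condition of relatedness. State there that relatedness to either drug is assessed under 6.2 only, and that agreement with the known profile bears on expectedness under 6.3.

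The cost is one deletion and one added sentence. More events may be classed as related, so reported drug-related rates may be slightly higher.

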4.2.2.2 Plerixafor Related Adverse Events

A grid of 20 horizontal black bars of varying lengths on a white background. The bars are arranged in a single row. The lengths of the bars are as follows: 1, 1. The first bar is the shortest, and the second bar is the longest.

4.3. Prohibited and/or Restricted Treatments

The following medications are prohibited during the study:

- Immunosuppressive agents unless they are utilized to treat an AE or as specified in **Sections 4.2 and 4.5**.
- Concurrent administration of any anticancer therapies (investigational or approved) with the exception of subjects in the survival period of the study.
- Use of growth factors unless prior discussion and agreement with the Protocol Chair.
- Use of allergen hyposensitization therapy

Palliative radiotherapy is permitted only under certain conditions as described in **Section 4.5**.

4.4. Other Restrictions and Precautions

Any vaccination containing attenuated or inactivated virus may be permitted if clinically indicated. However, this must be discussed and documented with the Protocol Chair prior to administration and may require a study drug washout period prior to and after administration of the vaccine. Inactivated influenza vaccination will be permitted on study without restriction.

It is the local imaging facility's responsibility to determine, based on subject attributes (e.g., allergy history, diabetic history and renal status), the appropriate imaging modality and contrast regimen for each subject. Imaging contraindications and contrast risks should be considered in this assessment. Subjects with renal insufficiency should be assessed as to whether or not they should receive contrast and if so, what type and dose of contrast is appropriate. Specific to MRI, subjects with severe renal insufficiency (i.e., estimated glomerular filtration rate (eGFR) < 30 mL/min/1.73m²) are at increased risk of nephrogenic systemic fibrosis.

4.5. Permitted Therapy

Subjects are permitted the use of topical, ocular, intra-articular, intranasal, and inhalational corticosteroids (with minimal systemic absorption). Immunosuppressive agents and the use of systemic corticosteroids are permitted in the context of treating AEs, prophylaxis prior to a diagnostic procedure (e.g., contrast MRI/CT scans) or as specified in **Section 4.2**. A brief course of corticosteroids for prophylaxis (e.g., contrast dye allergy) is permitted.

Subjects may continue to receive hormone replacement therapy (HRT).

Palliative and supportive care for disease-related symptoms may be offered to all subjects on the trial.

The potential for overlapping toxicities with radiotherapy and cemiplimab and plerixafor is currently not known. Therefore, palliative radiotherapy is not recommended while receiving any of these drugs, alone or in combination. If palliative radiotherapy in short courses and for isolated fields is required to control symptoms, then drug administration should be withheld, if possible, for at least 1 week before radiation and for at least 1 week after its completion. Subjects should be closely monitored for any potential toxicity during and after receiving radiotherapy. Prior to resuming study drug treatment, radiotherapy-related AEs should resolve to \leq Grade 1 or baseline and subjects must meet relevant dosing eligibility criteria. The Protocol Chair must be consulted prior to re-initiating treatment in a subject with a dosing interruption lasting $>$ 6 weeks after the last dose.

Details of palliative radiotherapy should be documented in the source records and electronic case report form (eCRF). Details in the source records should include: dates of treatment, anatomical site, dose administered and fractionation schedule, and AEs. Symptoms requiring palliative radiotherapy should be evaluated for objective evidence of disease progression. Subjects receiving palliative radiation of target lesions will have the evaluation of ORR just prior to radiotherapy but such subjects will no longer be evaluable for determination of response subsequent to the date palliative radiation occurs.

For subjects who need to undergo elective surgery (not tumor-related) during the study, it is recommended to hold study drug(s) for at least 2 weeks before and 2 weeks after surgery, or until the subject recovers from the procedure, whichever is longer. Prior to resuming study drug treatment, surgically-related AEs should resolve to ≤Grade 1 or baseline and subjects must meet relevant dosing eligibility criteria. The Protocol Chair must be consulted prior to re-initiating treatment in a subject with a dosing interruption lasting > 6 weeks after the last dose.

4.6. Definition of an Overdose for this Protocol

Overdose of cemiplimab or plerixafor is defined as:

An overdose is defined as the accidental or intentional administration of any dose of a product that is considered both excessive and medically important. Appropriate supportive treatment should be provided if clinically indicated.

All reports of overdose (with and without an AE) must be reported within 24 hours to the Protocol Chair and Sanofi as an SAE per **Section 6**.

4.7. Unacceptable Toxicity

Unacceptable toxicities are defined as any adverse event requiring permanent discontinuation per **Section 4.10.2** (exceptions for permanent discontinuation must be approved by the Protocol Chair).

If more than 1 of the first 6 patients experiences an unacceptable toxicity within the first cycle, then enrollment will be halted, and the overall risk-benefit ratio of the study will be reconsidered. At any time thereafter, if more than 33% of patients are observed to experience unacceptable toxicity within the first cycle, enrollment will be suspended until further review and consideration by the Protocol Chair. There will be no dose reductions for cemiplimab or plerixafor.

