4.10. Criteria for Removal from Treatment

The reason for study removal and the date the subject was removed will be documented in the CRF. A subject must be discontinued from the trial for any of the following reasons:

- The subject or legal representative (such as parent or legal guardian) withdraws consent.

A subject must be discontinued from treatment (but may continue to be monitored in the post-treatment follow-up portion of the trial) for any of the following reasons:

- The subject or legal representative (such as a parent or legal guardian) withdraws consent for treatment,
- Disease progression as defined in **Section 4.10.1**. If there are no signs of disease stabilization after 18 weeks of therapy, subjects should be discontinued,
- Intercurrent illness that prevents further administration of treatment,
- Severe or life-threatening cemiplimab- or plerixafor-related AE(s) (see **Section 4.10.2**),
- Need for >2 dose delays due to the same related toxicity as per the dose delay guidelines (see **Section 5.2**)
- If in the opinion of the Investigator, a change or temporal or permanent discontinuation of therapy would be in the best interest of the patient,
- Noncompliance with trial treatment or procedure requirements,
- Patient is lost to follow-up,
- Patient becomes pregnant, or
- Completed 24 months of treatment with cemiplimab and plerixafor. Note: 24 months of study medication is calculated from the date of the first dose.

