4.10.2. Cemiplimab- and Plerixafor-Related Adverse Events

Permanent discontinuation of all study treatment should be considered for any of the following (exceptions for permanent discontinuation must be approved by the Protocol Chair):

1. Severe or life-threatening related AEs, including, but not limited to, any of the following (the Protocol Chair must be notified in the event of these AEs):
 - Any grade 2 treatment-related uveitis, eye pain, or blurred vision that does not respond to topical therapy and does not improve to \leq Grade 1 severity within the re-treatment period OR requires systemic treatment
 - Any grade 3 non-skin, drug-related AE lasting > 7 days, with the following exceptions:
 - Grade 3 treatment-related uveitis, pneumonitis, bronchospasm, neurologic toxicity, hypersensitivity reaction, or infusion reaction of any duration requires discontinuation
 - Grade 3 treatment-related endocrinopathies adequately controlled with only physiologic hormone replacement do not require discontinuation
 - Grade 3 treatment-related laboratory abnormalities do not require treatment discontinuation except:

- Grade 3 treatment-related thrombocytopenia > 7 days OR that is associated with bleeding requires discontinuation
 - Any treatment-related liver function test (LFT) abnormality that meets the following criteria require discontinuation:
 - ALT or AST $> 8 \times$ ULN, regardless of duration, or
 - ALT or AST $> 5 \times$ and $\leq 8 \times$ ULN, that fails to return to \leq Grade 1 within 2 weeks despite medical intervention, or
 - Total bilirubin $> 5 \times$ ULN, or
 - Potential drug-induced liver injury (DILI) event (**Section 6.5.5**)
- Any grade 4 treatment-related AE or laboratory abnormality, except for the following events which do not require discontinuation:
 - Grade 4 neutropenia ≤ 7 days
 - Grade 4 lymphopenia and leukopenia.
 - Isolated Grade 4 amylase or lipase abnormalities that are not associated with symptoms or clinical manifestations.
 - Isolated grade 4 electrolyte imbalances/abnormalities that are not associated with clinical sequelae and are corrected with supplementation/appropriate management within 72 hours of their onset.

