 - Grade 4 treatment-related endocrinopathy adverse events, such as adrenal insufficiency, ACTH deficiency, hyper- or hypothyroidism, or glucose intolerance, which resolve or are adequately controlled with physiologic hormone replacement (corticosteroids, thyroid hormones) or glucose-controlling agents, respectively, may not require discontinuation after discussion with and approval from the Protocol Chair.
- Any dosing interruption lasting > 6 weeks with the following exceptions:
 - Dosing interruptions to allow for prolonged steroid tapers to manage drug-related adverse events are allowed. Prior to re-initiating treatment in a subject with a dosing interruption lasting > 6 weeks, the Protocol Chair must be consulted. Tumor assessments should continue as per protocol even if dosing is interrupted. Periodic study visits to assess safety and laboratory studies should also continue every 6 weeks or more frequently if clinically indicated during such dosing delays.
 - Dosing interruptions > 6 weeks that occur for non-drug-related reasons may be allowed if approved by the Protocol Chair. Prior to re-initiating treatment in a subject with a dosing interruption lasting > 6 weeks, the Protocol Chair

must be consulted. Tumor assessments should continue as per protocol even if dosing is interrupted. Periodic study visits to assess safety and laboratory studies should also continue every 6 weeks or more frequently if clinically indicated during such dosing delays.

- Any AE, laboratory abnormality, or intercurrent illness which, in the judgment of the Investigator, presents a substantial clinical risk to the subject with continued dosing.

In order to standardize the management of irAEs for all subjects, treatment management algorithms can be found in the NCCN's guidelines for the management of immunotherapy-related toxicities. Additional AE treatment management guidance included in the IBs might be considered for individual cases.

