- 1: If necessary, a scheduled cycle may be delayed for up to 1 week. Longer delays to be approved by the Protocol Chair.
- 2: Order of administration is Cemiplimab followed by Plerixafor. Subjects should be observed for a minimum of 30 minutes between each infusion. Plerixafor will be administered as a continuous 7-day IV infusion. Prepared plerixafor formulation is stable for 5 days at room temperature. Therefore, patients will return to clinic on day 4 to exchange the infusion bag and on day 8 to discontinue their plerixafor infusion.
- 3: Cancer history includes: primary site of cancer, gross location of primary tumor, secondary sites of cancer, histology, histologic grade, date of initial diagnosis, date of metastatic diagnosis, prior cancer therapy regimens, MSI testing, and tumor mutation testing. If MSI testing has not been previously done, MSI testing may be done retrospectively if tissue is available.
- 4: Complete physical examination and assessment of ECOG PS will be completed at baseline; focused physical examinations and assessment of ECOG PS will be conducted thereafter. Exams, concomitant medication, AE assessments, and ECOG PS can be evaluated up to 3 days prior to infusion on Day 1 of each cycle.
- 5: Blood pressure, pulse, and temperature. On Day 1 of each cycle, vitals should be collected prior to both the Cemiplimab and Plerixafor administrations. On Cycle 1 Day 1, patients will have a 6 hour observation period with hourly vital sign assessment.
- 6: Height will be obtained at or prior to baseline only.
- 7: Clinical hematology: CBC with differential ANC, ALC, AEC, and platelet count; serum chemistry: sodium, potassium, chloride, bicarbonate, glucose, BUN, creatinine, ALT, AST, alkaline phosphatase, total bilirubin, total protein, albumin, calcium, magnesium, and phosphorus. Calculated creatinine clearance (Cockcroft-Gault) is required at screening and on Day 1 of every cycle.
- 8: TSH (Total T3 and free T4 if TSH abnormal and clinically indicated).
- 9: Day 1 and 4 of Cycle 1 and 2 only
- 10: Bilirubin, blood, glucose, ketones, leukocytes, nitrite, pH, color, protein, RBC and WBC count, and specific gravity.
- 11: HIV antibody, hepatitis B surface antigen and hepatitis C antibody; additional virology may also be evaluated. Subjects who are hepatitis C antibody positive and confirmed negative viral load at screening will be allowed to enroll.

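### Does the toxicity stopping rule break down because it does not say whether the onset or the completion of a duration-defined toxicity must fall in Cycle 1?

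*Combined protocol and SAP*

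**What the plan says.** The rule appears in Sections 1.4, 4.7 and 12.2, each time limited to the first cycle. The run-in condition in 4.7 reads "If more than 1 of the first 6 patients experiences an unacceptable toxicity within the first cycle". After the run-in, enrolment stops whenever more than 33% of patients have had such an event, with the boundary tabulated in 12.2.

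The counted event is defined in 4.7: "Unacceptable toxicities are defined as any adverse event requiring permanent discontinuation per" Section 4.10.2. A parenthesis in that same sentence says exceptions need the Protocol Chair's approval.

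Several items in 4.10.2 depend on elapsed time:

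- "Any grade 3 non-skin, drug-related AE lasting > 7 days", with listed exceptions
- grade 3 thrombocytopenia beyond 7 days, unless bleeding makes it count at once
- grade 4 neutropenia, exempt only up to 7 days
- ALT or AST above 5 and up to 8 times ULN that has not fallen to "Grade 1 within 2 weeks despite medical intervention"
- grade 2 eye events that do not improve to "Grade 1 severity within the re-treatment period OR requires systemic treatment"
- "Any dosing interruption lasting > 6 weeks with the following exceptions"

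Footnote 1 of the study calendar (Section 9) adds "If necessary, a scheduled cycle may be delayed for up to 1 week", and longer with the Protocol Chair's approval. Section 4.10 opens its list with "A subject must be discontinued from treatment (but may continue to be monitored" in follow-up), while the lead-in to 4.10.2 says only that permanent discontinuation should be considered.

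**The concern.** A 21-day window is applied to events that may take longer than the rest of the window to qualify. Take a related grade 3 non-skin, non-laboratory event that starts on Day 17 and lasts 10 days. It counts if dated by onset, but not if the criterion must be met by Day 21. In the run-in, one patient decides the outcome, because 1 of 6 continues and 2 of 6 halts. This is the plan's only numerical safety rule for halting enrolment, so two teams applying it to the same patients could disagree.

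Three further points seemed to add to this. The end of Cycle 1 is unclear when Cycle 2 is late. The plan does not spell out whether an event excused by the Protocol Chair counts. The lead-ins of 4.10 and 4.10.2 differ in force, although 4.7 relies on discontinuation being required.

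**Working it through.** **Inputs.** Cycle length of 21 days (1.4, Table 1). Boundary in 12.2: 2 events at patient 6, 3 at patients 7–9, 4 at 10–12, and so on to 13 at 37–39. Printed operating characteristics in 12.2, from 5000 simulations. Durations from 4.10.2.

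**Step 1: reproduce the plan's table.** Let f(n,k) be the probability of reaching patient n with k events and no stop. Then f(n,k) = f(n−1,k)(1−p) + f(n−1,k−1)p. From n = 6, all probability at or above the boundary is removed and counted as stopped. Expected N = Σ n·P(stop at n) + 39·P(no stop).

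| Risk | Stop, printed | Stop, exact | E(N), printed | E(N), exact |
|---|---|---|---|---|
| 0.10 | 12.4% | 13.0% | 34.98 | 34.78 |
| 0.20 | 45.8% | 44.4% | 24.64 | 25.10 |
| 0.25 | 63% | 62.6% | 19.62 | 19.79 |
| 0.30 | 78.7% | 78.7% | 15.25 | 15.10 |
| 0.33 | 85% | 86.2% | 13.02 | 12.79 |
| 0.40 | 96.3% | 96.3% | 9.04 | 9.06 |

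At risks of 0.45 to 0.60 the printed and exact stopping probabilities differ by at most 0.1 point. The boundary and table are correct for whatever event is counted.

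**Step 2: what completion dating could remove.** An event starting on day t meets a d-day criterion on day t + d. With onset assumed uniform over Days 1–21, completion by Day 21 requires:

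- more-than-7-day items: t ≤ 14, so 14/21 = 67%
- the 2-week item: t ≤ 7, so 7/21 = 33%

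Let w be the share of events that qualify only through a more-than-7-day item. Counted risk = onset-dated risk × (1 − w/3). At an onset-dated risk of 0.30:

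| w | Counted risk | Stop, exact | Halt at patient 6 | E(N), exact |
|---|---|---|---|---|
| 0 | 0.300 | 78.7% | 58.0% | 15.1 |
| 0.25 | 0.275 | 71.1% | 52.4% | 17.3 |
| 0.5 | 0.250 | 62.6% | 46.6% | 19.8 |
| 1 | 0.200 | 44.4% | 34.5% | 25.1 |

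The run-in figure is 1 − (1−p)⁶ − 6p(1−p)⁵. For p = 0.30 this is 1 − 0.1176 − 0.3025 = 0.580.

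**Step 3: how far the assumptions carry this.** Both drug infusions fall on Days 1–7 (Table 1). If onsets fell on Days 1–8, which is equally an assumption, the latest more-than-7-day event would qualify on Day 8 + 7 = Day 15. All 8 of 8 onset days would then be captured, so the loss for these items is zero. The row w = 1 also needs no event to qualify at once. Yet 4.10.2 lists many immediate triggers: most grade 4 events, ALT or AST above 8 times ULN, bilirubin above 5 times ULN, and grade 3 pneumonitis or infusion reaction of any duration.

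**Step 4: which reading the documents support.**

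- Section 6.2 records an adverse event that changes grade as one event at its highest grade, and the forms in Appendices D and E carry an onset date. Both fit placing the event where it began.
- A dosing interruption beyond 6 weeks is not itself an adverse event, and 4.7 counts adverse events. It therefore does not belong in the list of toxicities that outlast the window.
- The exception clause sits in the 4.7 definition. An excused event does not require discontinuation, so it is most naturally not counted.
- Section 5.2 holds all study drugs for related AST or ALT above 3 times ULN. An open 5-to-8-times event would therefore normally delay Cycle 2. If Cycle 1 is taken to run until Cycle 2 starts, that event resolves or qualifies within it.
- Under onset dating, an event from Day 21 is settled by Day 21 + 7 = Day 28, or Day 21 + 14 = Day 35. It is counted late, not lost.

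**The case for a change.** The strongest reply is that none of this is written down. Onset dating is inferred, and completion dating can only reduce the count, so any error would favour continuing enrolment. Under 4.7 the Protocol Chair both approves exceptions and reviews a suspension. Settling the dating rule after an ambiguous event would let knowledge of the count influence the choice. A sentence or two would remove the doubt.

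What stands is that the text is silent and that the direction of the effect is as stated. It is also true that the re-treatment period is undefined, and that the lead-ins of 4.10 and 4.10.2 differ and must be reconciled by the sponsor. Neither point has been shown to alter a count, since most individual items say outright whether discontinuation is required.

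What does not stand is the step from silence to a faulty rule. No stated rule has been shown to give a wrong result. After the run-in the limit applies at any time, not at fixed looks. Unacceptable toxicities go to the Protocol Chair within 24 hours of being identified (6.5.1), safety meetings are planned weekly or as enrolment requires (11.2), and a Safety Monitoring Committee adds oversight beyond the Chair (11.3). Crossing the boundary leads to a halt and a review, so a late-qualifying event would come before people able to weigh it.

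**Conclusion.** No change follows. This is missing detail that a trial team would fill sensibly: place the event by its onset in Cycle 1, count it once its criterion is met, and leave out events excused under the 4.7 definition. On that reading the counted risk is the risk in the 12.2 table, and the table reproduces within 1.4 points for stopping and within 0.5 patient for expected size.

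Under the opposite reading the effect runs from zero (onsets on Days 1–8, more-than-7-day items) to the plan's own step from 78.7% to 45.8% (onset-dated risk 0.30, uniform onset, every event duration-only). The documents give neither an onset pattern nor a mix of events, so no point in that range can be defended as the likely one. The conclusion rests on onset dating being applied consistently.
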